## **10.3 Study Termination**

Although KBP Biosciences Co., Ltd. has every intention of completing the study, KBP Biosciences Co., Ltd. reserves the right to discontinue the study at any time for clinical or administrative reasons.

The end of the study is defined as the date on which the last patient completes the final end of study assessment.

## **10.4 Final Report**

Whether the study is completed or prematurely terminated, the Sponsor will ensure that the clinical study reports are prepared and provided to the regulatory agency as required by the applicable regulatory requirement(s). The Sponsor will also ensure that the clinical study reports in marketing applications meet the standards of the ICH harmonised tripartite guideline E3: Structure and content of clinical study reports.

Where required by applicable regulatory requirements, an Investigator signatory will be identified for the approval of the clinical study report. The Investigator will be provided reasonable access to statistical tables, figures, and relevant reports and will have the opportunity to review the complete study results.

Upon completion of the clinical study report, the Sponsor will provide the Investigator with the full summary of the study results. The Investigator is encouraged to share the summary results with the study patients, as appropriate. The study results will be posted on publicly available clinical trial registers.

## **12 Appendices**

### **12.1 Appendix: Schedule of Events**

**Table 12-1 Schedule of Events for Part 1**

Day	Screening	Patients Resident at CRU											Outpatient Visits						EOS 	
	-28 to -2	-1	Day 1 to Day 2											3	4	5	6	8	10	12
Hours		-24	0	2	4	6	8	10	12	18	24	48	72	96	120	168	216	264	312	
Admission to CRU		X																		
Discharge from CRU											X									
Informed Consent	X																			
Eligibility Assessment	X	X																		
Medical History	X																			
Demographics	X																			
Height (cm), Weight (kg), BMI	X																			
Previous Medications	X	X																		
Concomitant Medications			X																	
Physical Examination	X	X 																		X
Single 12-lead ECG 	X		X			X														X
Vital Signs (BP, PR, RR, T) 	X	X	X	X	X	X	X		X		X	X	X	X	X	X	X	X	X	X
AE Assessment	X	X	X																	
Clinical Laboratory Samples 	X	X				X					X 	X 	X 	X 	X 	X 	X 	X 	X 	X
Dose Administration			X																	
PK Blood Samples 			X	X	X	X	X	X	X	X	X	X	X	X	X	X	X	X	X	X
Biomarker Samples  (Aldosterone and Potassium)			X	X		X			X		X	X	X	X	X	X	X	X	X	X
HIV, Hepatitis B and C Screen	X																			
Drug/Alcohol Screen 	X	X 																		
Serum/Urine Pregnancy Test 	X	X																		X

AE= adverse event; BP = blood pressure; CRU = clinical research unit; ECG = electrocardiogram; EOS = end of study; HIV = human immunodeficiency virus; PR = pulse rate; PK = pharmacokinetics; RR = respiratory rate; T = temperature.  
 Note: baseline is the Day 1 predose (time 0) sample.

Brief physical examination will be conducted at Check-in (Day -1).

Patient should be resting in a semi-recumbent position for at least 5 minutes prior to ECG.

Blood pressure, heart rate, respiratory rate and oral temperature will be measured in patients in a semi-recumbent position for at least 5 minutes.

Clinical laboratory samples include: hematology, clinical chemistry, liver function, and urinalysis.

Laboratory samples for only creatinine will be collected at 24, 48, 72, 96, 120, 168, 216, and 264 hours postdose.

Blood samples for the determination of KBP-5074 concentrations and corresponding PK analysis will be collected at the following time points (All PK samples will be collected within  $\pm 5$  minutes of the nominal time unless otherwise specified): predose (at time 0 [-5 min], collected immediately prior to dosing) and 2, 4, 6, 8, 10, 12, 18, 24, 48, 72, 96, 120, 168, 216, 264, and 312 hours post dose.

Serum and plasma samples for biomarkers (aldosterone and serum potassium) will be collected at the following time points (All biomarker samples will be collected within  $\pm 5$  minutes of the nominal time unless otherwise specified): predose (at time 0 [-5 min], collected immediately prior to dosing) and 2, 6, 12, 24, 48, 72, 96, 120, 168, 216, 264, and 312 hours post dose.

Urine or salivary drug test performed at Screening and Check-in (Day -1).

Alcohol test (via Breathalyzer) is performed at Check-in (Day -1).

For female patients, urine or serum pregnancy test must be negative to enroll in the study. Patients who have a false positive test attributable to their post-menopausal state or kidney disease, as determined by the Investigator, will be allowed to participate.

End-of-study assessment will be performed after PK blood draw on Day 14 or upon withdrawal/dismissal of a patient from the study.

**Table 12-2 Schedule of Events for Part 2**

Day	Screening	Patients Resident at CRU																				Outpatient Visits						EOS 				
	-28 to -2	-1	1						2						3						4	5	6	8	10	12	14					
Hours		-24	0	2	4	6	8	10	12	18	24	44	44.25	44.5	45	46	47	48	48.5	49	50	52	72	96	120	168	216	264	312			
Admission to CRU		X																														
Discharge from CRU																							X 									
Informed Consent	X																															
Eligibility Assessment	X	X																														
Medical History	X																															
Demographics	X																															
Height (cm), Weight (kg), BMI	X																															
Previous Medications	X	X																														
Concomitant Medications			X																													
Physical Examination	X	X 																												X		
Single 12-lead ECG 	X		X			X																								X		
Vital Signs (BP, PR, RR, T) 	X	X	X	X	X	X	X		X		X							X							X	X	X	X	X	X	X	X
AE Assessment	X	X	X																													
Clinical Laboratory Samples 	X	X				X																								X		
Dose Administration 			X																													

Day	Screening	Patients Resident at CRU																				Outpatient Visits						EOS 		
	-28 to -2	-1	1						2						3						4	5	6	8	10	12	14			
Hours		-24	0	2	4	6	8	10	12	18	24	44	44.25	44.5	45	46	47	48	48.5	49	50	52	72	96	120	168	216	264	312	
PK Blood Samples 			X	X	X	X	X	X	X	X	X	X	X	X		X	X	X	X	X	X	X	X	X	X	X	X	X	X	X
Dialysate Sampling 													X	X	X	X	X													
Biomarker Samples (Aldosterone and Potassium) 			X	X		X			X		X												X	X	X	X	X	X	X	X
HIV, Hepatitis B and C Screen	X																													
Drug/Alcohol Screen 	X	X 																												
Serum/Urine Pregnancy Test 	X	X																												X

AE= adverse event; BP = blood pressure; CRU = clinical research unit; ECG = electrocardiogram; HIV = human immunodeficiency virus; PR = pulse rate; PK = pharmacokinetics; RR = respiratory rate; T = temperature.

Note: baseline is the Day 1 predose (time 0) sample.

Patients in Part 2 will be discharged from the CRU after the dialysate collection on Day 3.

Brief physical examination will be conducted at Check-in (Day -1).

Patient should be resting in a semi-recumbent position for at least 5 minutes prior to ECG.

Blood pressure, heart rate, respiratory rate and oral temperature will be measured in patients in a semi-recumbent position for at least 5 minutes.

Clinical laboratory samples include: hematology, clinical chemistry, liver function, and urinalysis.

Dosing will be based on the post dialysis weight from the last dialysis session prior to dosing.

Blood samples for the determination of KBP-5074 concentrations and PK analysis will be collected relative to dose administration as follows (All PK samples will be collected within ±5 minutes of the nominal time unless otherwise specified):

- During the interdialytic interval (using a venous stick or cannula) immediately predose (at time 0 [-5 min]; collected immediately prior to dosing, but following the termination of a previous dialysis session), 2, 4, 6, 8, 10, 12, 18, and 24 hours postdose;
- During the second HD session at 44 (immediately prior to HD [using a venous stick or cannula; -5 min] and 5 minutes after the start of HD [inlet {arterial; ±1 min} and outlet {venous; ±1 min} samples]), 44.25, 44.5, 46, and 47 hours postdose, and at the end of the second HD session;
- Following dialysis (using a venous stick or cannula) at 48.5, 49, 50, 52, 72, 96, 120, 168, 216, 264, and 312 hours postdose.

Cumulative dialysate will be collected and weight/volume determined for the following intervals: 44 to 44.5 hours, 44.5 to 45 hours, 45 to 46 hours, 46 to 47 hours, and 47 to 48 hours postdose. The dialysate collection will end at the end of dialysis (rather than at 48 hours) if a patient has dialysis for <4 hours. An additional sample may be collected until the end of dialysis for sessions lasting longer than 4 hours. The cumulative volume of dialysate collected during each interval will be documented. A 25 mL aliquot will be collected at the end of each interval for determination of KBP-5074 concentration.

Serum and plasma samples for biomarkers (aldosterone and serum potassium) will be collected at the following time points (All biomarker samples will be collected within  $\pm 5$  minutes of the nominal time unless otherwise specified): predose (at time 0 [-5 min], collected immediately prior to dosing) and 2, 6, 12, 24, 48, 72, 96, 120, 168, 216, 264, and 312 hours post dose.

Hemodialysis patients will be tested with a serum drug screen at Screening and using salivary testing at Check-in (Day -1).

Alcohol test (via Breathalyzer) is performed at Check-in (Day -1).

For female patients, urine or serum pregnancy test must be negative (to accommodate dialysis patients) to enroll in the study. Patients who have a false positive test attributable to their post-menopausal state or kidney disease, as determined by the Investigator, will be allowed to participate.

End-of-study assessment will be performed after PK blood draw on Day 14 or upon withdrawal/dismissal of a patient from the study.

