**Figure 3-3 Study Design Schematic for Part 2 (Tuesday, Thursday, Saturday HD Schedule)**

Abbreviations: CRU = clinical research unit; HD = hemodialysis; PK = pharmacokinetic.  
 Note: hemodialysis days are represented in red text.

Patients in Part 1 and Part 2 will be screened to enter the study within 28 days (Day -28 to Day -2) prior to administration of KBP-5074 on Day 1. Eligible patients in Part 1 and Part 2 will be admitted to the CRU at Check-in (Day -1) and will undergo baseline assessments. Patients will remain confined from Check-in (Day -1) until 24 hours postdose for Part 1 and 52 hours postdose for Part 2 and PK and safety assessments will be performed during outpatient visits through the end of study assessment on Day 14.

Patients who withdraw prematurely from the study may be replaced at the discretion of the Investigator and KBP Biosciences Co., Ltd. to ensure that 12 patients complete the study (6 patients in each of Cohorts 1 and 2, in Parts 1 and 2, respectively).

Study assessments including physical examination findings, vital signs (blood pressure, pulse rate, respiratory rate and oral temperature), 12-lead ECGs, clinical laboratory findings, monitoring of AEs, and PK blood sampling will be performed at either screening, Check-in (Day -1), or after KBP-5074 dosing through the end of study assessment. Adverse events and serious adverse events (SAEs) will be assessed from the time the patient signs the informed consent form until exit from the study. A schedule of events for Part 1 and Part 2 is presented in [Table 12-1](#) and [Table 12-2](#), respectively.

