### 5.2 Treatments Administered

All doses of KBP-5074 will be administered orally to patients at the CRU. Administration of each dose of study drug will be supervised, verified (see [Section 5.7](#)), and documented according to the CRU's standard operating procedures. The actual date and time of each dose administration will be entered in the eCRF.

In Part 1 of the study, non-HD patients with severe CKD in Cohort 1 will receive a single oral capsule dose of 0.5 mg KBP-5074 with up to 240 mL of room temperature water on Day 1 following a fast between 2 and 4 hours. The exact amount of water consumed will be recorded in the eCRF.

In Part 2 of the study, HD patients with severe CKD will receive a single 0.5 mg oral capsule dose of KBP-5074 with up to 240 mL of room temperature water following a fast between 2 and 4 hours. The exact amount of water consumed with the dose of KBP-5074 will be recorded in the eCRF. The dose of KBP-5074 will be administered on Day 1 immediately following a dialysis session.

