### Clinical Laboratory Tests

All laboratory data will be summarized by study part and cohort, and at each scheduled timepoint using descriptive statistics (n, mean, SD, median, minimum, and maximum).

The baseline value is the last value observed prior to first administration of study drug and any information taken after first administration of study drug is regarded as post baseline

information. The change-from-baseline variables will be calculated as the post-baseline value minus the value at baseline. Change from baseline on continuous data will be summarized using descriptive statistics at each scheduled time point by cohort. For categorical data, change-from-baseline will be summarized using frequency and proportion at each scheduled timepoint by cohort.

Individual data listings of laboratory results will be presented for each patient. Values outside of the laboratory's reference range (i.e, those with low or high values) will be flagged in the laboratory listings.

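### In Part 2 the 6 h laboratory change from baseline spans the Day 1 dialysis session, because no panel is scheduled at the stated time 0 baseline

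*Protocol*

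**What the plan says.** Three parts of the protocol bear on the Part 2 laboratory baseline.

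- **The schedule.** The note under Table 12-2 states "baseline is the Day 1 predose (time 0) sample". The laboratory panel is defined there by a footnote: "Clinical laboratory samples include: hematology, clinical chemistry, liver function, and urinalysis". Its row is marked at Screening, Day -1, 6 h and end of study.
- **The analysis rule.** Section 7.7.2, Clinical Laboratory Tests, states "The baseline value is the last value observed prior to first administration of study drug", and adds "Change from baseline on continuous data will be summarized using descriptive statistics at each scheduled time point by cohort". Section 3.1 also places baseline work a day earlier: patients "will be admitted to the CRU at Check-in (Day -1) and will undergo baseline assessments".
- **The dosing sequence.** Section 5.2 states for Part 2: "The dose of KBP-5074 will be administered on Day 1 immediately following a dialysis session".

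The biomarkers, aldosterone and serum potassium, have their own schedule in Table 12-2: "predose (at time 0 [-5 min], collected immediately prior to dosing) and 2, 6, 12, 24, 48, 72" hours and later.

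**The concern.** The schedule note points to a laboratory sample that is not scheduled. The rule in section 7.7.2 fills the gap with the Day -1 value. In Part 1 that does no particular harm, because nothing comparable happens between Day -1 and the dose. In Part 2 a dialysis session falls in between, so a pre-dialysis value becomes the reference for a post-dialysis sample.

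Safety and tolerability form a primary objective, and laboratory change from baseline is one of the planned safety summaries. Part 2 has only two post-dose panels, at 6 h and at 312 h. Section 1.3 reports a fasted time to maximum concentration of 4 to 7 h, so the 6 h panel is the only full panel near peak exposure. For a given dialysed analyte, every Part 2 patient would be shifted in the same direction. With no control group, averaging cannot remove that shift. An analysis plan can choose among collected values, but it cannot supply a time 0 panel that was never drawn.

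**Working it through.** The protocol gives no figure for this point, so there is none to reproduce. The check is a reading of the schedule followed by an order-of-magnitude calculation for one analyte.

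**1. Early columns of Table 12-2**

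| Row | Screening | Day -1 | 0 h | 2 h | 4 h | 6 h |
|---|---|---|---|---|---|---|
| Clinical laboratory | X | X | – | – | – | X |
| 12-lead ECG | X | – | X | – | – | X |
| Vital signs | X | X | X | X | X | X |
| Biomarkers | – | – | X | X | – | X |

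ECG, vital signs and biomarkers all carry a time 0 mark; the laboratory panel does not. No footnote lists the panel's times, so this rests on column position. In the extracted text some later columns of both schedule tables drift against their footnotes. The early columns used here align, but the cell should be confirmed on the original page.

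**2. Which value the rule selects**

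Before the dose, panel values exist at Screening and Day -1. The last of these is Day -1.

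**3. What lies between that baseline and the 6 h panel**

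Day -1 panel → Day 1 dialysis session → dose at time 0 → 6 h panel. The 6 h change therefore holds the effect of the session, any recovery after it, and any drug effect. One open-label cohort cannot separate them.

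**4. Size, for urea only**

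Input: KT/V of at least 1.2 (inclusion criterion 5). In a single-pool model without generation or fluid removal, post/pre = exp(−Kt/V).

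- At 1.2: exp(−1.2) = 0.301, a fall of 69.9%.
- Variant allowing for generation and fluid removal: Kt/V = −ln(R − 0.008t) + (4 − 3.5R) × UF/W, with R = post/pre, t = 4 h (the approximate session length in section 3.1.1) and an assumed fluid removal UF/W of 0 to 4% of body weight. The fall is 66.7% at 0 and 63.2% at 4%.
- Part of the fall may be regained by 6 h. Assuming 10% to 30% of it, the simple model gives 0.699 × 0.90 = 62.9% to 0.699 × 0.70 = 48.9% below Day -1.

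On these assumptions, 6 h urea would be tabulated at roughly half or less of baseline with no drug effect.

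**5. Potassium**

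The biomarker schedule has a time 0 sample, drawn after dialysis and before the dose. It is later than the Day -1 panel, so the last-value rule in sections 7.7.2 and 7.7.3 selects it. The 6 h potassium change then starts from a post-dialysis value.

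**6. Day 14**

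Day -1 is at −24 h and Day 14 at 312 h. The gap is 312 + 24 = 336 h, or exactly 14 days. If the weekly schedule is regular, both fall at the same point of the dialysis week, so Day -1 is a fair reference for Day 14. The difficulty is confined to 6 h.

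**The case against.** The strongest case against acting is that little depends on this output. It is one descriptive column in 6 patients, no formal safety analysis is planned, and no decision rule in the protocol uses the 6 h mean change. Individual results are listed with range flags, and abnormal results become adverse events on the Investigator's judgement. All of this is correct and lowers the importance. It does not make the tabulated change interpretable.

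The table note can also be read as covering only assessments that have a time 0 entry. That would remove the contradiction in wording, but the laboratory baseline would still be Day -1.

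A sample taken minutes after dialysis is an imperfect baseline too, because post-dialysis rebound would remain in the 6 h change. That stands: the remedy takes the session itself out of the comparison but not the recovery from it.

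A reader might infer that a drug effect on potassium would be hidden. The documents do not support this. Potassium has a post-dialysis time 0 sample and serial follow-up, and the baseline rule selects that sample. What remains is narrower: potassium is also in the chemistry panel (Table 6-1), and the protocol does not say outright that the time 0 value serves as baseline in the laboratory summary as well.

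**Conclusion.** The point holds for the Part 2 change at 6 h in dialysis-sensitive chemistry such as urea, creatinine, phosphorus and CO2, and possibly in blood counts and proteins. That change is confounded by the Day 1 session. Part 1, the Day 14 comparison and the potassium analysis are not materially affected.

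A reader might go further and infer that the 6 h laboratory change measures dialysis instead of the drug across the whole panel. That is too strong. The change contains both effects, and Table 6-1 also lists liver enzymes, bilirubin and lipids, for which the protocol gives no ground to expect a large dialysis effect. The figure of about 70% likewise applies to urea only. It is an illustration from the entry criterion and should not be carried over to other analytes.

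The conclusion rests on the empty time 0 cell in the laboratory row and on the dialysis-then-dose sequence in section 5.2. The urea range also rests on the assumed fluid removal and regain. This is worth correcting because a primary safety objective would otherwise carry a misleading summary, but its reach is modest.

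**What to change.** - In Table 12-2, add the chemistry and hematology panel to the time 0 draw already made after dialysis and before dosing for PK and biomarkers.
- In section 7.7.2, state that in Part 2 this panel is the baseline for the 6 h change and that Day -1 is the reference for Day 14.
- If no panel is added, present the Part 2 6 h laboratory values without change from baseline.
- Reconcile the note under Table 12-2 with section 7.7.2, and state that the time 0 sample is the potassium baseline wherever potassium is summarized.

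The cost is one extra tube in 6 patients and a few words in two places. The drawbacks are two reference points in the Part 2 laboratory tables and some post-dialysis rebound left in the 6 h change, which the table should note. No sample size figure changes.
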